5.1. Analysis Principles

Statistical analysis will be conducted after database is locked and performed using SAS software version 9.4 or higher according to this statistical analysis plan (SAP). If statistical analysis methods are changed, it will be described in the final clinical study report.

Continuous variables will be summarized by the descriptive statistics (number (n), mean, standard deviation (SD), median, minimum and maximum). Categorical variables will be presented in frequency and percentage (with the percentage excluding the number missing in the denominator).

In case of statistical hypothesis testing, two-sided tests will be conducted at a 5% significance level and the p-value of each test result will be presented in the summary table.

Statistical Analysis Plan for rPMS

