5.2.2. Handling of Missing and Incomplete dates

Missing or incomplete dates will be handled by following rule:

	Missing	Imputation
Date of initial diagnosis	DD	01
	MM/DD	01/01
	YYYY/MM/DD	No imputation
End date of administration for study drug	'Ongoing'	Date of final follow-up

6. Statistical Analyses

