 - Discontinuation (permanently, temporarily or delayed)
 - Dosage reduced
 - Dosage increased
 - No change
 - Unknown
 - Not applicable
- 3) Occurrence status of adverse events by demographic and other baseline characteristics
 - The incidence of adverse events and 95% CI will be presented by categorical variables of demographic and other baseline characteristics.
 - To identify statistically significant difference in incidence of adverse events by categorical variables of demographic and other baseline characteristics, Chi-square test (χ^2 test) or Fisher's exact test (if the expected frequency for each cell under 5 is more than 20%) will be performed.
- 4) Analysis of factors that affect the safety
 - In the re-examination report, logistic regression or multivariate analysis will be performed and an odds ratio with 95% CI and p-value will be presented to identify the factors that affect incidence of adverse events in demographic and other baseline characteristics.
- 5) Analysis for special patient populations [pediatric subjects (aged < 19 years), geriatric subjects (aged \geq 65 years), subjects with renal impairment, subjects with hepatic impairment]
 - Adverse events and adverse drug reactions collected in each special patient population will be presented the number of subjects having adverse events, incidence of adverse events and the number of adverse events for each SOC and PT.
- 6) Analysis for population except from safety analysis
 - Adverse events and adverse drug reactions collected in population except from safety analysis will be presented the number of subjects having adverse events, incidence of adverse events and the number of adverse events for each SOC and PT.

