	≥ 65 years	xxx	xxx(xx.xx)	[xx.xx, xx.xx]	x.xxxx
	< 65 years	xxx	xxx(xx.xx)	[xx.xx, xx.xx]	
Classification	Total	xxx	xxx(xx.xx)	-	
	Outpatient	xxx	xxx(xx.xx)	[xx.xx, xx.xx]	x.xxxx
	Inpatient	xxx	xxx(xx.xx)	[xx.xx, xx.xx]	
	Total	xxx	xxx(xx.xx)	-	

¹⁾Chi-square Test

²⁾Fisher's Exact Test

*Statistically significant

Programming note: This table is repeated for each sub-group with the following table title and footnote.

Title : [Table 23-x] Occurrence status of adverse events by demographic characteristics (sub-group x: N=xxx)

Footnote: Sub-group 1: Subjects who are first administered INLYTA® during the study period

Sub-group 2: Subjects who has continued administration of INLYTA® since the time prior to the contract date

[Table 24] Occurrence status of adverse events by other baseline characteristics

Factor	Classification	No. of Subjects	Incidence of AE n(%)	[95% CI]	p-value ¹⁾²⁾
Duration of aRCC	Category 1	xxx	xxx(xx.xx)	[xx.xx, xx.xx]	x.xxxx
	Category 2	xxx	xxx(xx.xx)	[xx.xx, xx.xx]	
	Category 3	xxx	xxx(xx.xx)	[xx.xx, xx.xx]	
	...	xxx	xxx(xx.xx)	[xx.xx, xx.xx]	
	Total	xxx	xxx(xx.xx)	-	
Cell component of aRCC	Clear cell	xxx	xxx(xx.xx)	[xx.xx, xx.xx]	x.xxxx
	Other	xxx	xxx(xx.xx)	[xx.xx, xx.xx]	
	Total	xxx	xxx(xx.xx)	-	
Metastasis	Yes [§]	xxx	xxx(xx.xx)	[xx.xx, xx.xx]	x.xxxx
	Liver	xxx	xxx(xx.xx)	[xx.xx, xx.xx]	
	Lung	xxx	xxx(xx.xx)	[xx.xx, xx.xx]	
	Bone	xxx	xxx(xx.xx)	[xx.xx, xx.xx]	
	Brain	xxx	xxx(xx.xx)	[xx.xx, xx.xx]	
	Skin	xxx	xxx(xx.xx)	[xx.xx, xx.xx]	
	Lymph nodes	xxx	xxx(xx.xx)	[xx.xx, xx.xx]	
	Other	xxx	xxx(xx.xx)	[xx.xx, xx.xx]	
	No	xxx	xxx(xx.xx)	[xx.xx, xx.xx]	
	Total	xxx	xxx(xx.xx)	-	
Primary lesion surgery	Done	xxx	xxx(xx.xx)	[xx.xx, xx.xx]	x.xxxx
	Not done	xxx	xxx(xx.xx)	[xx.xx, xx.xx]	
	Total	xxx	xxx(xx.xx)	-	

Dummy Table

Factor	Classification	No. of Subjects	Incidence of AE n(%)	[95% CI]	p-value ¹⁾²⁾
	Total	xxx	xxx(xx.xx)	-	
Medical history	Yes	xxx	xxx(xx.xx)	[xx.xx, xx.xx]	x.xxxx
	No	xxx	xxx(xx.xx)	[xx.xx, xx.xx]	
	Total	xxx	xxx(xx.xx)	-	
Renal impairment	Yes	xxx	xxx(xx.xx)	[xx.xx, xx.xx]	x.xxxx
	No	xxx	xxx(xx.xx)	[xx.xx, xx.xx]	
	Total	xxx	xxx(xx.xx)	-	
Hepatic impairment	Yes	xxx	xxx(xx.xx)	[xx.xx, xx.xx]	x.xxxx
	No	xxx	xxx(xx.xx)	[xx.xx, xx.xx]	
	Total	xxx	xxx(xx.xx)	-	
Allergic history	Yes	xxx	xxx(xx.xx)	[xx.xx, xx.xx]	x.xxxx
	No	xxx	xxx(xx.xx)	[xx.xx, xx.xx]	
	Total	xxx	xxx(xx.xx)	-	
Prior chemotherapy	Yes	xxx	xxx(xx.xx)	[xx.xx, xx.xx]	x.xxxx
	No	xxx	xxx(xx.xx)	[xx.xx, xx.xx]	
	Unknown	xxx	xxx(xx.xx)	[xx.xx, xx.xx]	

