	Total	xxx	xxx(xx.xx)	-	
Prior immunotherapy	Yes	xxx	xxx(xx.xx)	[xx.xx, xx.xx]	x.xxxx
	No	xxx	xxx(xx.xx)	[xx.xx, xx.xx]	
	Unknown	xxx	xxx(xx.xx)	[xx.xx, xx.xx]	
	Total	xxx	xxx(xx.xx)	-	
Prior radiation therapy	Yes	xxx	xxx(xx.xx)	[xx.xx, xx.xx]	x.xxxx
	No	xxx	xxx(xx.xx)	[xx.xx, xx.xx]	
	Unknown	xxx	xxx(xx.xx)	[xx.xx, xx.xx]	
	Total	xxx	xxx(xx.xx)	-	
Concomitant medication	Yes	xxx	xxx(xx.xx)	[xx.xx, xx.xx]	x.xxxx
	No	xxx	xxx(xx.xx)	[xx.xx, xx.xx]	
	Total	xxx	xxx(xx.xx)	-	
Duration of administration	Category 1	xxx	xxx(xx.xx)	[xx.xx, xx.xx]	x.xxxx
	Category 2	xxx	xxx(xx.xx)	[xx.xx, xx.xx]	
	Category 3	xxx	xxx(xx.xx)	[xx.xx, xx.xx]	
	...	xxx	xxx(xx.xx)	[xx.xx, xx.xx]	
	Total	xxx	xxx(xx.xx)	-	
Daily average dose	Category 1	xxx	xxx(xx.xx)	[xx.xx, xx.xx]	x.xxxx
	Category 2	xxx	xxx(xx.xx)	[xx.xx, xx.xx]	
	Category 3	xxx	xxx(xx.xx)	[xx.xx, xx.xx]	
	...	xxx	xxx(xx.xx)	[xx.xx, xx.xx]	
	Total	xxx	xxx(xx.xx)	-	

¹⁾Overlapped

²⁾Chi-square Test

²⁾Fisher's Exact Test

*Statistically significant

Programming note: This table is repeated for each sub-group with the following table title and footnote.

Title : [Table 24-x] Occurrence status of adverse events by other baseline characteristics (sub-group x: N=xxx)

Footnote: Sub-group 1: Subjects who are first administered INLYTA® during the study period

Sub-group 2: Subjects who has continued administration of INLYTA® since the time prior to the contract date

Dummy Table

[Table 25] Multivariate logistic regression for occurrence status of adverse events

Factor	Classification	Estimate	Standard Error	p-value	Odds Ratio	[95% CI]
Intercept		xx.xx	xx.xx	x.XXXX		
Factor 1	Yes	xx.xx	xx.xx	x.XXXX	xx.xx	[xx.xx, xx.xx]
	No	Reference				
Factor 2	Category 1	Reference				
	Category 2	xx.xx	xx.xx	x.XXXX	xx.xx	[xx.xx, xx.xx]
...						
...						

Response variable: occurrence status of adverse events

*Statistically significant

Programming note1: This analysis will be performed in the re-examination report only.

Programming note2: This table is repeated for each sub-group with the following table title and footnote.

Title : [Table 25-x] Multivariate logistic regression for occurrence status of adverse events (sub-group x: N=xxx)

Footnote: Sub-group 1: Subjects who are first administered INLYTA® during the study period

Sub-group 2: Subjects who has continued administration of INLYTA® since the time prior to the contract date

[Table 26] Best overall response and objective response rate

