	25th percentile [95% CI)	xx.xx[xx.xx, xx.xx)

[figure not shown]
Programming note: This table is repeated for each sub-group with the following table title and footnote.

Title : [Table 28-x] Summary statistics for time to progression (sub-group x: N=xxx)

Footnote: Sub-group 1: Subjects who are first administered INLYTA® during the study period

Sub-group 2: Subjects who has continued administration of INLYTA® since the time prior to the contract date

[Figure 2] Kaplan-Meier curve for time to progression

Programming note: This table is repeated for each sub-group with the following table title and footnote.

Title : [Figure 2-x] Kaplan-Meier curve for time to progression (sub-group x: N=xxx)

Footnote: Sub-group 1: Subjects who are first administered INLYTA® during the study period

Sub-group 2: Subjects who has continued administration of INLYTA® since the time prior to the contract date

Dummy Table

[Table 29] Objective response rate by demographic characteristics

Factor	Classification	No. of Subjects	Objective Response Rate n(%)	[95% CI]	p-value ¹⁾²⁾
Sex	Male	xxx	xxx(xx.xx)	[xx.xx, xx.xx]	x.xxxx
	Female	xxx	xxx(xx.xx)	[xx.xx, xx.xx]	
	Total	xxx	xxx(xx.xx)	-	
Age	Category 1	xxx	xxx(xx.xx)	[xx.xx, xx.xx]	x.xxxx
	Category 2	xxx	xxx(xx.xx)	[xx.xx, xx.xx]	
	Category 3	xxx	xxx(xx.xx)	[xx.xx, xx.xx]	
	...	xxx	xxx(xx.xx)	[xx.xx, xx.xx]	
	Total	xxx	xxx(xx.xx)	-	
Pediatric	< 19 years	xxx	xxx(xx.xx)	[xx.xx, xx.xx]	x.xxxx
	≥ 19 years	xxx	xxx(xx.xx)	[xx.xx, xx.xx]	
	Total	xxx	xxx(xx.xx)	-	
Geriatric	≥ 65 years	xxx	xxx(xx.xx)	[xx.xx, xx.xx]	x.xxxx
	< 65 years	xxx	xxx(xx.xx)	[xx.xx, xx.xx]	
	Total	xxx	xxx(xx.xx)	-	
Classification	Outpatient	xxx	xxx(xx.xx)	[xx.xx, xx.xx]	x.xxxx
	Inpatient	xxx	xxx(xx.xx)	[xx.xx, xx.xx]	
	Total	xxx	xxx(xx.xx)	-	

¹⁾Chi-square Test

²⁾Fisher's Exact Test

*Statistically significant

Programming note: This table is repeated for each sub-group with the following table title and footnote.

Title : [Table 29-x] Objective response rate by demographic characteristics (sub-group x: N=xxx)

Footnote: Sub-group 1: Subjects who are first administered INLYTA® during the study period

Sub-group 2: Subjects who has continued administration of INLYTA® since the time prior to the contract date

[Table 30] Objective response rate by demographic and other baseline characteristics

Factor	Classification	No. of Subjects	Objective Response Rate n(%)	[95% CI]	p-value ¹⁾²⁾
Duration of aRCC	Category 1	xxx	xxx(xx.xx)	[xx.xx	x.xxxx

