	Category 2	xxx	xxx(xx.xx)	[xx.xx, xx.xx]	
	Category 3	xxx	xxx(xx.xx)	[xx.xx, xx.xx]	
	...	xxx	xxx(xx.xx)	[xx.xx, xx.xx]	
	Total	xxx	xxx(xx.xx)	-	
Cell component of aRCC	Clear cell	xxx	xxx(xx.xx)	[xx.xx, xx.xx]	x.xxxx
	Other	xxx	xxx(xx.xx)	[xx.xx, xx.xx]	
	Total	xxx	xxx(xx.xx)	-	
Metastasis	Yes [§]	xxx	xxx(xx.xx)	[xx.xx, xx.xx]	x.xxxx
	Liver	xxx	xxx(xx.xx)	[xx.xx, xx.xx]	
	Lung	xxx	xxx(xx.xx)	[xx.xx, xx.xx]	
	Bone	xxx	xxx(xx.xx)	[xx.xx, xx.xx]	
	Brain	xxx	xxx(xx.xx)	[xx.xx, xx.xx]	
	Skin	xxx	xxx(xx.xx)	[xx.xx, xx.xx]	
	Lymph	xxx	xxx(xx.xx)	[xx.xx, xx.xx]	
	nodes				
	Other	xxx	xxx(xx.xx)	[xx.xx, xx.xx]	
	No	xxx	xxx(xx.xx)	[xx.xx, xx.xx]	

Dummy Table

Factor	Classification	No. of Subjects	Objective Response Rate n(%)	[95% CI]	p-value ¹⁾²⁾
	Total	xxx	xxx(xx.xx)	-	
Primary lesion surgery	Done	xxx	xxx(xx.xx)	[xx.xx, xx.xx]	x.xxxx
	Not done	xxx	xxx(xx.xx)	[xx.xx, xx.xx]	
	Total	xxx	xxx(xx.xx)	-	
Medical history	Yes	xxx	xxx(xx.xx)	[xx.xx, xx.xx]	x.xxxx
	No	xxx	xxx(xx.xx)	[xx.xx, xx.xx]	
	Total	xxx	xxx(xx.xx)	-	
Renal impairment	Yes	xxx	xxx(xx.xx)	[xx.xx, xx.xx]	x.xxxx
	No	xxx	xxx(xx.xx)	[xx.xx, xx.xx]	
	Total	xxx	xxx(xx.xx)	-	
Hepatic impairment	Yes	xxx	xxx(xx.xx)	[xx.xx, xx.xx]	x.xxxx
	No	xxx	xxx(xx.xx)	[xx.xx, xx.xx]	
	Total	xxx	xxx(xx.xx)	-	
Allergic history	Yes	xxx	xxx(xx.xx)	[xx.xx, xx.xx]	x.xxxx
	No	xxx	xxx(xx.xx)	[xx.xx, xx.xx]	
	Total	xxx	xxx(xx.xx)	-	
Prior chemotherapy	Yes	xxx	xxx(xx.xx)	[xx.xx, xx.xx]	x.xxxx
	No	xxx	xxx(xx.xx)	[xx.xx, xx.xx]	
	Unknown	xxx	xxx(xx.xx)	[xx.xx, xx.xx]	
	Total	xxx	xxx(xx.xx)	-	
Prior immunotherapy	Yes	xxx	xxx(xx.xx)	[xx.xx, xx.xx]	x.xxxx
	No	xxx	xxx(xx.xx)	[xx.xx, xx.xx]	
	Unknown	xxx	xxx(xx.xx)	[xx.xx, xx.xx]	
	Total	xxx	xxx(xx.xx)	-	
Prior radiation therapy	Yes	xxx	xxx(xx.xx)	[xx.xx, xx.xx]	x.xxxx
	No	xxx	xxx(xx.xx)	[xx.xx, xx.xx]	
	Unknown	xxx	xxx(xx.xx)	[xx.xx, xx.xx]	
	Total	xxx	xxx(xx.xx)	-	
Concomitant medication	Yes	xxx	xxx(xx.xx)	[xx.xx, xx.xx]	x.xxxx
	No	xxx	xxx(xx.xx)	[xx.xx, xx.xx]	
	Total	xxx	xxx(xx.xx)	-	
Duration of administration	Category 1	xxx	xxx(xx.xx)	[xx.xx, xx.xx]	x.xxxx
	Category 2	xxx	xxx(xx.xx)	[xx.xx, xx.xx]	
	Category 3	xxx	xxx(xx.xx)	[xx.xx, xx.xx]	
	...	xxx	xxx(xx.xx)	[xx.xx, xx.xx]	
	Total	xxx	xxx(xx.xx)	-	
Daily average dose	Category 1	xxx	xxx(xx.xx)	[xx.xx, xx.xx]	x.xxxx
	Category 2	xxx	xxx(xx.xx)	[xx.xx, xx.xx]	
	Category 3	xxx	xxx(xx.xx)	[xx.xx, xx.xx]	
	...	xxx	xxx(xx.xx)	[xx.xx, xx.xx]	
	Total	xxx	xxx(xx.xx)	-	

[§]Overlapped

¹⁾Chi-square Test

²⁾Fisher's Exact Test

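### SAP Tables 24 and 30 test exposure accrued during follow-up as if it were a baseline characteristic, so a significance flag on those rows does not show a factor that affects adverse events or response

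*SAP*

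**What the plan says.** SAP 6.2 item 3 plans chi-square or Fisher tests "To identify statistically significant difference in incidence of adverse events by categorical variables of demographic and other baseline characteristics". SAP 6.3 item 4 plans the same for ORR. Under SAP 5.1, "two-sided tests will be conducted at a 5% significance level".

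The shells name the factors. Table 24 is titled "Occurrence status of adverse events by other baseline characteristics" and Table 30 "Objective response rate by demographic and other baseline characteristics". Both have rows for "Duration of administration", "Daily average dose" and concomitant medication, each with a p-value cell, and both carry the footnote "Statistically significant". SAP 6.4 repeats the tests in each sub-group.

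The definitions are elsewhere:

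- **Duration and average dose.** SAP 6.1.6 sums duration from the first to the last treatment period and divides total dose by that duration. In SAP 5.2.2 the row "End date of administration for study drug" replaces an ongoing entry with the date of final follow-up.
- **Concomitant medication.** Protocol 3.4 gives it a baseline role but refers to 3.5.4 for the definition. Section 3.5.4.7 covers drugs in use at enrolment and drugs started afterwards. The shells show one yes/no row.

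SAP 6.2 item 4 and 6.3 item 5 then plan regressions to find what affects AE incidence and ORR among demographic and other baseline characteristics. Tables 25 and 31 name no covariates.

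**The concern.** A baseline factor is known before the outcome can occur. Duration and average dose are not, and for AEs the dependence runs both ways. A patient treated for longer has more time in which an AE or a response can be recorded. An AE can also end treatment, change the dose or lead to a new drug. SAP 6.2 lists discontinuation and dose change among the AE actions, and protocol 5.2.1 counts an abnormal test as an AE when it leads to a dosing change, discontinuation or significant added drug treatment.

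Neither document sets a landmark, an exposure adjustment or a caution for these rows. A baseline title combined with a significance flag invites a risk-factor reading in a safety report to the regulator. The dose row can point the wrong way: if AEs lead to dose cuts, patients with low average dose will show more AEs.

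**Working it through.** **Inputs.** From the documents: 5% two-sided tests (SAP 5.1), at least 100 subjects (SAP 2.4), and AE reporting to at least 28 days after last dose (protocol 5.1.2). Neither document gives an AE rate, treatment duration, stopping rate, dose-change rate or scan timing. There is no planned figure to reproduce, and everything below is an assumption. In every case the factor has no effect.

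**Duration against any AE, by hand.** Assume exponential treatment duration with median 6 months, so μ = ln 2 / 6 = 0.1155 per month. The AE hazard λ is constant and the same for everyone, AEs never stop treatment, and AEs are collected for f months after treatment. Then

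P(AE | duration d) = 1 − exp(−λ(d + f)).

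Split duration into thirds, bounded at survival fractions 1, 2/3, 1/3 and 0, and let r = (μ + λ)/μ. For the third between fractions a and b,

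P(AE) = 1 − (3/r) · exp(−λf) · (a^r − b^r), and overall P(AE) = 1 − exp(−λf)/r.

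With λ = 0.1 and f = 28/30.4375 = 0.92: r = 1.866, (3/r) · exp(−0.092) = 1.467, (2/3)^r = 0.469, (1/3)^r = 0.129.

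- Shortest third: 1 − 1.467 × 0.531 = 0.22
- Middle third: 1 − 1.467 × 0.340 = 0.50
- Longest third: 1 − 1.467 × 0.129 = 0.81
- Overall: 0.51

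The noncentrality of the 2-df chi-square is (100/3) × Σ(p_k − p)² / [p(1 − p)] = 33.3 × (0.0837 + 0.0001 + 0.0900) / 0.2499 ≈ 23. Against a critical value of 5.99, a flag is almost certain.

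With 12 months of follow-up (f = 12) the multiplier is 0.484. The thirds become 0.74, 0.84 and 0.94, with 0.84 overall. The noncentrality is 33.3 × (0.0091 + 0.0000 + 0.0098) / 0.135 ≈ 4.7, so a flag appears about half the time.

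**Simulated over wider settings** (same model, N = 100, the SAP's chi-square/Fisher rule, simulation error of a few points):

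| Assumption | AE incidence | Runs flagged |
|---|---|---|
| No AE-driven stopping, follow-up 28 days | 33–79% | about 97–100% |
| No AE-driven stopping, follow-up 6–12 months | 48–84% | about 50–83% |
| 40% of on-treatment AEs stop treatment, 28 days | 33–91% | about 57–82% |
| 80% of AEs stop treatment, or nearly all patients have an AE | – | about 6–14%, lower still at about 99% incidence |

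If AEs come early (falling hazard), the direction depends on stopping. At 48% incidence, AE frequency in the shortest and longest thirds is 32% and 64% with no stopping, but 65% and 38% with 80% stopping.

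**The other rows**

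- **Average dose against AE.** If half of the patients with an AE have the dose lowered and nothing else changes it, 13–63% of runs are flagged at 33–85% incidence. At 70% incidence, AEs appear in 77% of the lowest-dose third and 56% of the highest.
- **Concomitant medication against AE.** If half of the patients with an AE start a drug, 15–75% are flagged at 51–85% incidence, with 50–85% of patients already on a drug at first dose.
- **Duration against ORR.** 10–94% are flagged when no AE stops treatment and at most half of those stopping before the first scan are scanned. If all are scanned, 3–6%.
- **Average dose and concomitant medication against ORR.** 0–23% and 2–11%.

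**Control.** First recorded dose, or drugs in use at first dose, is flagged in 1–7% of runs. The test holds its level; the choice of variable causes the inflation.

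**The case against.** The strongest reply is that SAP 6.2 item 3 and 6.3 item 4 ask only whether incidence or ORR differs between categories. Recorded incidence can truly differ by duration, so rejecting that null is not an error. This stands. The rates above are false positives only for the reading that the factor affects the outcome.

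The SAP also partly separates these variables. Table 2, its own list of other baseline characteristics, leaves out duration and dose, which sit in Table 7, and the text of 6.1 names medication and exposure apart from baseline characteristics. But 6.1.5 and 6.1.6 fall under the 6.1 baseline heading, and Tables 24 and 30 put the rows under a baseline title.

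The study is mainly descriptive (protocol 3.9), and protocol 3.12 says the regulator's guideline governs the SAP. That lowers the stakes but does not make a flag on these rows interpretable.

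Three stronger readings are tempting, and the documents do not support them:

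- **All three variables are set during follow-up.** Concomitant medication includes drugs in use at enrolment. In Sub-group 1 these can be true baseline values. In Sub-group 2 enrolment comes after treatment began, so even they may post-date first dose.
- **These variables will enter the regressions.** Tables 25 and 31 leave the factors unnamed, so entry is possible, not certain.
- **A false flag is nearly certain.** That needs no AE-driven stopping and short follow-up. Protocol 5.1.2 sets 28 days as a minimum, and longer follow-up weakens the effect.

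**Conclusion.** Wrong as written, but minor. Duration of administration and daily average dose are post-baseline variables tested and flagged under a baseline title. Concomitant medication is a mixture. A flag on these rows cannot be read as a factor that affects AEs or, mainly for duration, ORR.

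The inflation runs from none to very large. Its size depends on AE-driven stopping, follow-up after treatment and AE incidence, none of which the documents give. The direction can also reverse when AEs come early. A reader of the report therefore could not correct for it. The calculations assume 100 patients and no true effect, and do not model entry to Sub-group 2 part-way through treatment. The exploratory rows, and any regression that takes them in, are affected; the overall AE, ORR, PFS and TTP summaries are not.

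**What to change.** 1. In Tables 24 and 30, move duration of administration and daily average dose under a heading such as *Exposure during study, descriptive only*, with no p-value or flag. The rows remain if the regulator's format needs them.
2. Make the concomitant-medication row descriptive. A test may be kept only for Sub-group 1, limited to drugs whose recorded start date is on or before first dose. It cannot be rescued for Sub-group 2: protocol 3.5.4.7 does not ask for drugs stopped before enrolment, so use at first dose may be missed without being recorded as unknown.
3. State in SAP 6.2 item 4 and 6.3 item 5 that covariates for Tables 25 and 31 are limited to variables known at first dose, for example first recorded dose.

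The cost is a few table-shell edits and one SAP sentence, with no new data: dose periods and medication start dates are already collected (protocol 3.5.4.7 and 3.5.4.8). If the Sub-group 1 medication test is kept, it needs a rule for incomplete start dates, which SAP 5.2.2 lacks. The downside is that the exposure rows carry no p-value.

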## **5.2. DEFINITIONS OF SAFETY EVENTS**

### **5.2.1. Adverse events**

An AE is any untoward medical occurrence in a patient administered a medicinal product. The event need not necessarily have a causal relationship with the product treatment or usage. Examples of adverse events include but are not limited to:

- Abnormal test findings (see below for circumstances in which an abnormal test finding constitutes an adverse event);
- Clinically significant symptoms and signs;
- Changes in physical examination findings;
- Hypersensitivity;
- Lack of efficacy;

- Drug abuse;
- Drug dependency.

Additionally, for medicinal products, they may include the signs or symptoms resulting from:

- Drug overdose;
- Drug withdrawal;
- Drug misuse;
- Off-label use;
- Drug interactions;
- Extravasation;
- Exposure during pregnancy;
- Exposure during breast feeding;
- Medication error;
- Occupational exposure.

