2.4. Sample size Considerations

Per MFDS regulation, at least 3,000 subjects were required for the study initially. However, based on the decision from MFDS on April 26, 2018, at least 100 subjects who are eligible according to '2.3 Study Population' will be observed for total of 9 years.

3. Analysis Populations

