System Organ Class Preferred Term	xxx(xx.xx), [xxx]	[xx.xx, xx.xx]	xxx(xx.xx), [xxx]	[xx.xx, xx.xx]	
...	xxx(xx.xx), [xxx]	[xx.xx, xx.xx]	xxx(xx.xx), [xxx]	[xx.xx, xx.xx]	
Total	xxx(xx.xx), [xxx]	[xx.xx, xx.xx]	xxx(xx.xx), [xxx]	[xx.xx, xx.xx]	

[§]Overlapped, MedDRA latest version
E: Number of adverse events

Programming note: This table is repeated for each sub-group with the following table title and footnote.

Title : [Table 15-x] Adverse events and adverse drug reactions (sub-group x: N=xxx)

Footnote: Sub-group 1: Subjects who are first administered INLYTA® during the study period

Sub-group 2: Subjects who has continued administration of INLYTA® since the time prior to the contract date

[Table 16] Adverse events by their severity

System Organ Class [§] Preferred Term	Number of adverse events by their severity [†] (%)				
	Grade 1	Grade 2	Grade 3	Grade 4	Grade 5
System Organ Class Preferred Term	xxx(xx.xx)	xxx(xx.xx)	xxx(xx.xx)	xxx(xx.xx)	xxx(xx.xx)
...	xxx(xx.xx)	xxx(xx.xx)	xxx(xx.xx)	xxx(xx.xx)	xxx(xx.xx)
Total	xxx(xx.xx)	xxx(xx.xx)	xxx(xx.xx)	xxx(xx.xx)	xxx(xx.xx)

[§]MedDRA latest version

[†]Severity evaluation of adverse event must be done according to the NCI CTC grade

Programming note: This table is repeated for each sub-group with the following table title and footnote.

Title : [Table 16-x] Adverse events by their severity (sub-group x: N=xxx)

Footnote: Sub-group 1: Subjects who are first administered INLYTA® during the study period

Sub-group 2: Subjects who has continued administration of INLYTA® since the time prior to the contract date

Dummy Table

[Table 17] Adverse events by their outcome

System Organ Class [§] Preferred Term	Number of adverse events by their outcome (%)			
	Recovered	Recovered with sequelae	Recovering	Not recovered
System Organ Class				
Preferred Term	xxx(xx.xx)	xxx(xx.xx)	xxx(xx.xx)	xxx(xx.xx)
...	xxx(xx.xx)	xxx(xx.xx)	xxx(xx.xx)	xxx(xx.xx)
Total	xxx(xx.xx)	xxx(xx.xx)	xxx(xx.xx)	xxx(xx.xx)

§MedDRA latest version

Programming note: This table is repeated for each sub-group with the following table title and footnote.

Title : [Table 17-x] Adverse events by their outcome (sub-group x: N=xxx)

Footnote: Sub-group 1: Subjects who are first administered INLYTA® during the study period

Sub-group 2: Subjects who has continued administration of INLYTA® since the time prior to the contract date

Dummy Table

[Table 18] Adverse events by their seriousness

		Number of adverse events by their seriousness (%)						

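### The safety factor analysis tests and models only 'any adverse event', and severity is counted only per event, so the share of subjects with a Grade 3 or higher event is never reported

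*SAP*

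**What the plan says.** **Factor analysis.** SAP 6.2 item 3 gives the purpose of the univariate tests as "To identify statistically significant difference in incidence of adverse events by categorical variables of demographic and other baseline characteristics". Tables 23 and 24 have a single outcome column, the incidence of AEs. Item 4 adds a regression "to identify the factors that affect incidence of adverse events in demographic and other baseline characteristics", and the Table 25 footnote fixes the outcome: "Response variable: occurrence status of adverse events". No other safety outcome is tested or modelled by factor.

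**Severity.** Severity is among the safety endpoints (SAP 4.1, Protocol 3.5.3.1). Item 2 of SAP 6.2 summarises it as a frequency of events, and the Table 16 column heading is "Number of adverse events by their severity". Protocol 3.5.4.9.1 requires a separate entry, with its own dates, whenever the severity of an event changes.

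**Breadth of the outcome.** Protocol 5.2.1 states: "An AE is any untoward medical occurrence in a patient administered a medicinal product". All grades and causes are recorded.

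**Testing and size.** SAP 5.1 says "two-sided tests will be conducted at a 5% significance level". The default in SAP 6.2 is chi-square, with the exception "Fisher's exact test (if the expected frequency for each cell under 5 is more than 20%) will be performed". SAP 2.4 sets the size: "at least 100 subjects who are eligible according to '2.3 Study Population' will be observed for total of 9 years". SAP 6.4 repeats items 1-4 in each of the two sub-groups (newly treated, already on treatment).

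**The concern.** A yes/no outcome is informative about risk factors only if both classes are reasonably filled. The response here is at least one AE of any grade and any cause. It takes in mild symptoms, qualifying test findings and fatal progression, in patients with advanced cancer observed for at least 28 days and often through long treatment. If most subjects have at least one event, the AE-free minority carries nearly all the information. A report that no factor affects safety could then reflect the outcome chosen rather than the drug.

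The second part needs no assumption about rates. Table 16 counts records, and one episode that moves from Grade 2 to Grade 3 and back gives three of them. A reader cannot recover from that table how many subjects had a Grade 3 or higher event, and no other table gives the figure.

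**Working it through.** The plan states no power, effect size or AE rate, so there is no figure of its own to reproduce.

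**Inputs from the documents:** N = 100 (SAP 2.4); two-sided 5% (SAP 5.1); chi-square unless more than 20% of cells have an expected count below 5, then Fisher (SAP 6.2 item 3). In a 2x2 table one cell is 25%, so a single small cell triggers Fisher. With a 50:50 factor and k AE-free subjects, the expected AE-free count per half is k/2, so Fisher applies when k < 10.

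**Assumptions:** a binary factor split 50:50; a true odds ratio of 3; any-AE incidence q varied, because neither document gives it.

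**Step 1: power under the SAP's rule.** The two group rates solve (p1 + p2)/2 = q and p2/(1 - p2) = 3 x p1/(1 - p1). Power is the sum over a, b = 0..50 of Bin(a; 50, p1) x Bin(b; 50, p2) for every table whose p-value, by whichever test the rule selects for that table, is at most 0.05.

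| Average incidence q | p1 | p2 | Power |
|---|---|---|---|
| 50% | 0.3660 | 0.6340 | 79% |
| 60% | 0.4718 | 0.7282 | 76% |
| 80% | 0.7165 | 0.8835 | 57% |
| 88% | 0.8257 | 0.9343 | 39% |
| 92% | 0.8825 | 0.9575 | 20% |
| 95% | 0.9260 | 0.9740 | 6% |

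Using Fisher throughout would give 26% at 88% and 14% at 92%. That understates power under the plan, because the rule often selects chi-square there.

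**Step 2: smallest attainable p-value with 5 AE-free of 100.** Fisher applies. The most extreme table puts all five in one category.
- 50:50: 2 x C(50,5)/C(100,5) = 2 x 2,118,760/75,287,520 = 0.056. No table reaches 5%.
- 60:40, all five in the 40: C(40,5)/C(100,5) = 658,008/75,287,520 = 0.0087.
- 70:30, all five in the 30: 0.0019.

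Even 51:49 can reach significance if all five are in the 49: C(49,5)/C(100,5) = 1,906,884/75,287,520 = 0.025. The opposite tail, C(51,5)/C(100,5) = 0.031, is the more probable table and is not added. If the five all fall in the larger category, the p-value stays above 0.05 (0.0565 at 51:49, 0.081 at 60:40). The barrier is therefore specific to an even split.

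**Step 3: a sub-group of 50 (assumed size).** With 5 AE-free (90% incidence) and 25:25, the smallest p is 2 x C(25,5)/C(50,5) = 2 x 53,130/2,118,760 = 0.0501 (0.0502 before rounding up), just above 5%. At 30:20, with all five in the 20, it is 15,504/2,118,760 = 0.0073. Power at odds ratio 3 with 25:25 is 24% for 90% v 75% and 5% for 95% v 86%.

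**Step 4: the regression.** Tables 23 and 24 list 5 + 14 = 19 factors. At 90% and 95% incidence about 10 and 5 of 100 subjects are AE-free. If many factors were entered, separation and unstable odds ratios would be expected.

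**The case against.** **The ceiling is not documented.** This is fair. Protocol 3.1 mandates no visits, laboratory tests are optional (3.5.4.9.2), and AEs of patients already on treatment come from charts (3.5.4.9.1). Mild events may be missed and incidence may be well below 90%. At 80% the loss is moderate (57% power against 76-79%). The power argument is conditional and must be read that way.

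**Nothing could be detected.** A reader might infer that at 95% incidence significance is impossible. The documents do not support this in general. It holds for an even split, and few of the listed factors need split evenly: SAP section 1 puts clear cell at about 85% of RCC. Attainable is not the same as likely, however, and power at 95% remains very low in the case examined.

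**Harm is already reported per subject.** This is partly right. Tables 8-15 give subject-level counts for SAEs, ADRs and unexpected events, with 95% CIs in the SOC/PT tables. Tables 32-35 do so, without CIs, for AEs and ADRs in the special populations. Tables 10, 12 and 14 list severity for serious or unexpected events. A non-serious, expected Grade 3 event appears in none of these as a subject-level severity figure.

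**Any-AE should be replaced as the main tested outcome.** A reader might go this far too, but the Grade 3 or higher and SAE rates are equally unknown. By symmetry, an outcome at 12% or 8% incidence has the same 39% or 20% power in Step 1. Protocol 3.12 also says that the SAP follows the regulator's post-marketing guideline, and Protocol 3.9 describes mainly summary displays. Adding outcomes is defensible; replacing any-AE is a trade-off that the documents do not settle.

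**Conclusion.** The point holds in two parts.

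1. **Without any assumed rate:** any-AE is the only safety outcome tested or modelled by factor, and severity is tabulated only per event. The share of subjects with a Grade 3 or higher event is not reported and cannot be derived from Table 16.
2. **Conditional on a high any-AE rate:** the factor analysis has little information. For N = 100, a 50:50 factor and odds ratio 3, power falls from 76-79% at 50-60% incidence to 57% at 80%, 39% at 88%, 20% at 92% and 6% at 95%. Sub-group analyses suffer earlier.

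The documents do not establish that the rate is that high, nor that significance is out of reach for factors in general. The risk is that a null result is read as absence of effect. It is cheap to remove because grade and seriousness are already on the CRF.

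**What to change.** - **SAP 6.2 items 1-2, Tables 8 and 16:** add the number and percentage of subjects by worst grade, and the subject-level incidence with 95% CI of Grade 3 or higher AEs and ADRs.
- **SAP 6.2 items 3-4, Tables 23-25:** repeat with at least one Grade 3 or higher AE and at least one SAE as additional responses. Keep the any-AE tables as planned.
- **Beside each test and regression:** show the number of subjects in the rarer outcome class, so that a non-significant result from a handful of subjects is not reported as no effect.

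**Cost:** SAP wording and a few extra tables, with no new data collection. The additional responses produce more p-values, which should be labelled exploratory.
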